V2	PPD [REDACTED]	Added the text “In all cases, the medical judgment of the Investigator’s is taken into account. In particular, if the Investigator’s clinical response assessment – that takes into account the overall medical judgment of the specific patient’s case - is not in agreement with the exact application of the clinico-haematological ELN or EUMNET response criteria , the Investigator’s assessment will supersede the “mathematical” application of these criteria and used for analysis into study report.” to the following sections: Section 16.3, Sections 17.2, 18.1 and 18.2. But section 16.11: sub section “EVALUATION OF PRELIMINARY EFFICACY ACCORDING TO THE REVISED ELN CRITERIA” and Section 19.1 the word updated from “clinico-haematological ELN or EUMNET response criteria ” to “revised clinico-haematological ELN response criteria”
V2	PPD [REDACTED]	Section 5.2: ITT population definition updated
V2	PPD [REDACTED]	Section 15.1: Compliance derivation equation updated.
V2	PPD [REDACTED]	Section 16.2. EFFICACY ASSESSMENT; the LOCF section removed because study is not using LOCF method to

Document: PPD [REDACTED]

Author: PPD [REDACTED]

Version Number:

V2.2

Version Date:

21 March 2018

Template No: CS_TP_BS016 – Revision 3

Reference: CS_WI_BS005

Effective Date: 01May2012

Copyright © 2012 Quintiles Transnational Corp. All rights reserved.

The contents of this document are confidential and proprietary to Quintiles Transnational Corp. Unauthorized use, disclosure or reproduction is strictly prohibited.

		handle missing data.
V2	PPD	All Listing numbers changed from 16.1.x.x to 16.2.x.x to follow ICH E3 listing number guideline.
V2	PPD	The word of “exact method (as applicable)” added to the section 6.5
V2.1	PPD	The SAP section 10 updated to include following information in the table. Overall treatment group analysis for Part A tables and Figures, patients age group (< 60 years / ≥60 years), Patients requiring phlebotomy, Patients with previous thrombosis history, patients with age ≥ 60 years and/or previous thrombosis history, Controlled hypertension (i.e. Normal ranges for systolic blood pressure: less than 120 mmHg, diastolic blood pressure: less than 80mmHg) and Number of patients with Pruritus, Headache, Microvascular Symptoms. Corresponding tables are updated for Part A and Part B II.
V2.1	PPD	SAP section 19.1: Additional analysis of patients without the symptom of headache, pruritus and microvascular symptoms (i.e MPN SAF Score =0) and number and percentage of patient with symptom score from 0 to 3, from 4 to 6 and more than 7 are added. Also patients rate with normalized WBCs (WBCs count ≤ 10 x 10 ⁹ /L), Patients rate with normalized platelets (platelets ≤ 400 x 10 ⁹ /L) and Patients rate with normalized haematocrit (haematocrit <45% without phlebotomy) are added. The following tables/figures are added.

Document: PPD

Author: PPD

Version Number:

V2.2

Version Date:

21 March 2018

Template No: CS_TP_BS016 – Revision 3

Reference: CS_WI_BS005

Effective Date: 01May2012

Copyright © 2012 Quintiles Transnational Corp. All rights reserved.

The contents of this document are confidential and proprietary to Quintiles Transnational Corp. Unauthorized use, disclosure or reproduction is strictly prohibited.

		
Tables 14.2.5.1, 14.2.5.2, 14.2.5.3, 14.2.5.4 and figures 14.2.1.18, 14.2.1.19, 14.2.1.20, 14.2.1.21, 14.2.1.22, 14.2.1.23, and 14.2.1.24 are added for Part A.
 
Tables 14.2.6.3, 14.2.6.4, 14.2.6.5, 14.2.6.6 and figures 14.2.1.19, 14.2.1.20, 14.2.1.21, 14.2.1.22, 14.2.1.23, 14.2.1.24 and 14.2.1.25 are added for Part BII.

V2.1	PPD	
Section 20.4: Additional information of 'The number (n) and percentage (%) at baseline, Cycle 3 Day 28 and Cycle 6 Day 28 showed a Spleen Volume reduction \geq 35%' is added.
 
MedDRA dictionary (version 19.0) changed to MedDRA dictionary (version 20.1) and WHO-DRL Drug Dictionary (Version 01MAR2016) changed to WHO-DRL Drug Dictionary (Version 01SEP2017)
 
Section 15.1: '+1' removed from the Per visit" Compliance calculation formula.
 
Added the text 'Also for the last cycle compliance calculation this formula will be used as the last dose of study drug date considering from disposition page.'

V2.2 (Addendum)	PPD	
1. Analysis performed for mathematical application of ELN response criteria (not agreed by the medical site team) and following tables are added.
 
Part A: 14.2.1.1.1, 14.2.1.4.1, 14.2.1.7.1, 14.2.1.8.1, 14.2.1.9.1, 14.2.1.10.1
 
Part B: 14.2.1.1.1, 14.2.1.3.1, 14.2.2.1.1, 14.2.2.2.1, 14.2.2.3.1, 14.2.2.4.1, 14.2.9.1, 14.2.9.3, 14.2.2.7, 14.2.2.8.
 
2. The following tables/Figures are

Document: PPD

Author: PPD

Version Number: V2.2
 Version Date: 21 March 2018

Template No: CS_TP_BS016 – Revision 3
 Effective Date: 01May2012

Reference: CS_WI_BS005

		
added:- Part A: T14.3.5.3, T14.3.5.4, T14.2.5.5, T14.2.5.6, F14.2.1.25, F14.2.1.26 and T14.1.21.2 modified.
 
Part B: T14.3.5.3, T14.3.5.4, T14.2.6.7, 14.2.9.2, F14.2.1.26, F14.2.1.27 and T14.1.22.2 modified.
 
3. The following suffix number are added to TFLs outputs to differentiate the study parts in CSR: .a added for Part A, .bi added for Part B IA and .bii added for Part B II.

--	--	--

Document: PPD

Author: PPD

Version Number:

V2.2

Version Date:

21 March 2018

Template No: CS_TP_BS016 – Revision 3

Reference: CS_WI_BS005

Effective Date: 01May2012

Copyright © 2012 Quintiles Transnational Corp. All rights reserved.

The contents of this document are confidential and proprietary to Quintiles Transnational Corp. Unauthorized use, disclosure or reproduction is strictly prohibited.

LIST OF ABBREVIATIONS AND DEFINITION OF TERMS

AE	Adverse Event
ALP	Alkaline phosphatase
ALT	Alanine aminotransferase
AST	Aspartate aminotransferase
ATC	Anatomical Therapeutic Chemical Classification
AUC	Area under concentration-time curve
AUC _(0-τ)	Area under concentration-time curve over the dosing interval: from t=0 to t=12h
AUC _{last}	Area under concentration-time curve over the dosing interval: from t= 0 up to the last detectable concentration timepoint
b.i.d.	Bis In Die (twice daily)
BLQ	Below the lower limit of quantitation
BUN	Blood Urea Nitrogen
Ca	Calcium
CI	Confidence Intervals
Cl	Chloride
Clast	Last detectable plasma concentration
Cmax	Maximal plasma concentration
cMPN	chronic Myelo-Proliferative Neoplasms
CMO	Contract Manufacturing Organization
CR	Complete Response
CRF	Case Report Form
CRO	Contract Research Organization
CT	Computerized Tomography
CTCAE	Common Terminology Criteria for AE
Cτ	trough concentration (Pre-dose levels on day 28 in the cycles of treatment)
CV	Coefficient of Variation
DLT	Dose Limiting Toxicity

Document: PPD

Author: PPD

Version Number:

V2.2

Version Date:

21 March 2018

Template No: CS_TP_BS016 – Revision 3

Reference: CS_WI_BS005

Effective Date: 01May2012

Copyright © 2012 Quintiles Transnational Corp. All rights reserved.

The contents of this document are confidential and proprietary to Quintiles Transnational Corp. Unauthorized use, disclosure or reproduction is strictly prohibited.

ECG	Electrocardiogram
ECOG	Eastern Cooperative Oncology Group
ELN	European LeukemiaNet
ET	Essential Thrombocythemia
EU	European Union
EUMNET	European Myelofibrosis Network
Hb	Haemoglobin
HBV	Hepatitis B Virus
HCT	Haematocrit
HCV	Hepatitis C Virus
HDACs	Histone deacetylases
HDACi	Histone deacetylases inhibitors
HDPE	High-density Polyethylene
HIV	Human Immunodeficiency Virus
ICH	International Conference on Harmonization
ITT	Intent-to-treat
JAK2	Janus Kinase 2
JAK2 ^{V617F}	Janus Kinase 2 mutated at position 617
K	Potassium
LCM	Left Costal Margin
LDH	Lactate Dehydrogenase
MCH	Mean Corpuscular Haemoglobin
MCHC	Mean Corpuscular Haemoglobin Concentration
MCV	Mean Corpuscular Volume
MedDRA	Medical Dictionary for Regulatory Activities
MF	Myelofibrosis
mg	Milligram
Mg	Magnesium
MPN-SAF	Myeloproliferative Neoplasm Symptom Assessment Form

Document PPD

Author: PPD

Version Number:

V2.2

Version Date:

21 March 2018

Template No: CS_TP_BS016 – Revision 3

Reference: CS_WI_BS005

Effective Date: 01May2012

Copyright © 2012 Quintiles Transnational Corp. All rights reserved.

The contents of this document are confidential and proprietary to Quintiles Transnational Corp. Unauthorized use, disclosure or reproduction is strictly prohibited.

MRI	Magnetic Resonance Imaging
msec	Millisecond
MTD	Maximum Tolerated Dose
Na	Sodium
NCI	National Cancer Institute
nM	Nanomolar
NR	No Response
NYHA	New York Heart Association
NQ	Not quantifiable
o.d.	Once Daily
PD	Pharmacodynamic
PLT	Platelets count
PMF	Primary Myelofibrosis
PP	Per-protocol
PR	Partial Response
PT	Preferred Term
PV	Polycythemia Vera
PK	Pharmacokinetics
QOL	Quality Of Life
qRT-PCR	Quantitative Real Time Polymerase Chain Reaction
QTc	QT interval corrected
RBC	Red Blood Cell count
RT-PCR	Real Time Polymerase Chain Reaction
RR	Response Rate
SAE	Serious Adverse Event
SAP	Statistical Analysis Plan
SAS	Statistical Analysis System
SOC	System Organ Class
SUSAR	Suspected Unexpected Serious Adverse Reaction

Document: PPD

Author: PPD

Version Number:

V2.2

Version Date:

21 March 2018

Template No: CS_TP_BS016 – Revision 3

Reference: CS_WI_BS005

Effective Date: 01May2012

Copyright © 2012 Quintiles Transnational Corp. All rights reserved.

The contents of this document are confidential and proprietary to Quintiles Transnational Corp. Unauthorized use, disclosure or reproduction is strictly prohibited.

STAT5	Signal Transducers and Activators of Transcriptase 5
TdP	Torsades de Pointes
TEAE	Treatment-Emergent Adverse Event
t.i.d.	Ter In Die (three times daily)
T _{max}	Time of the maximal concentration in plasma
T _{last}	Time of the last detectable concentration in plasma
ULN	Upper Limit of Normal

1. INTRODUCTION

This document describes the rules and conventions to be used in the presentation and analysis for the Study N.: DSC/12/2357/45 (hereinafter “Study”).

It describes the data to be summarised and analyzed, including specifics of the statistical analyses to be performed. Deviations from methods described in the statistical analysis plan might appear. In case of such deviations the reason for the deviation will be stated in the final statistical report.

This Statistical Analysis Plan (SAP) is based on the Study protocol (version 1.0, dated 01st March 2013), Amended Protocol (version 3.0, dated 29 July 2015) and on two Amendments (Amendment 1, dated 23rd July 2013 and Amendment 2 dated 29th July 2015).

Notably, for the purpose of this document the name “Givinostat” is used to indicate the whole Study drug name “Givinostat hydrochloride monohydrate” (also known as ITF2357, i.e. its Sponsor’s research code). Therefore, the dosages/concentrations of the Study drug are expressed as Givinostat hydrochloride monohydrate.

2. STUDY OBJECTIVES

In recent years several reports have documented that histone deacetylases inhibitors (HDACi) induce neoplastic cells to undergo growth arrest, differentiation and/or apoptotic cell death. Among these agents, Givinostat (Sponsor’s research code: ITF2357) has most recently demonstrated effects on haematological parameters as well as constitutional parameters in patients with Polycythemia Vera (PV).

Preliminary signs of clinical activity in patients with JAK2 mutant cMPN, have been observed in two studies with Givinostat (Studies N.: DSC/07/2357/28 and DSC/08/2357/38). In these studies, the maximum administered dose of Givinostat was 150 mg per day which was generally well tolerated. Assuming a linear relationship between dose and efficacy, greater clinical efficacy could be expected with increased doses of Givinostat.

Since the Maximum Tolerated Dose (MTD) of Givinostat has not been defined previously, the first aim of the current Study (**Part A**, Phase Ib) is, therefore, to determine the MTD of Givinostat in patients with PV. This Study will investigate the safety, tolerability, pharmacokinetic (PK), and pharmacodynamic (PD) activity of Givinostat monotherapy. As such, the Study will characterize Dose Limiting Toxicities (DLTs) and MTD of Givinostat.

Document: PPD

Author: PPD

Version Number:

V2.2

Version Date:

21 March 2018

Template No: CS_TP_BS016 – Revision 3

Reference: CS_WI_BS005

Effective Date: 01May2012

Copyright © 2012 Quintiles Transnational Corp. All rights reserved.

The contents of this document are confidential and proprietary to Quintiles Transnational Corp. Unauthorized use, disclosure or reproduction is strictly prohibited.

The second aim of the Study (**Part B**, Phase II) is to characterize the clinical efficacy of Givinostat at the MTD.

2.1. PRIMARY OBJECTIVE

This is a two-part, multicentre, open label, non-randomized, phase Ib/II study to assess the safety and tolerability, MTD and preliminary efficacy of Givinostat in patients with JAK2^{V617F} positive PV.

Part A is the dose escalation portion of the Study; and, once the MTD is established, **Part B** is commenced where the preliminary efficacy of Givinostat in PV patients is to be established. Patients are enrolled either in **Part A** or **Part B** and transition from one part to the other is not allowed.

PART A

- To characterize the safety, tolerability and MTD of Givinostat in patients with PV.

PART B

- To evaluate the preliminary efficacy of Givinostat at the MTD after 3 cycles according to the clinico-haematological European LeukemiaNet (ELN) response criteria [\[1\]](#).
- To determine the safety and tolerability of Givinostat at the MTD after 3 cycles.

2.2. SECONDARY OBJECTIVES

PART A

- To evaluate the preliminary efficacy of Givinostat after 3 and 6 cycles of treatment according to the clinico-haematological ELN response criteria [\[1\]](#).
- To characterize PK.

PART B

- To evaluate the preliminary efficacy of Givinostat at the MTD after 6 cycles according to the clinico-haematological ELN response criteria [\[1\]](#).
- To determine the safety and tolerability of Givinostat at the MTD after 6 cycles.
- To characterize PK.

Document: PPD

Author: PPD

Version Number:

V2.2

Version Date:

21 March 2018

Template No: CS_TP_BS016 – Revision 3

Reference: CS_WI_BS005

Effective Date: 01May2012

Copyright © 2012 Quintiles Transnational Corp. All rights reserved.

The contents of this document are confidential and proprietary to Quintiles Transnational Corp. Unauthorized use, disclosure or reproduction is strictly prohibited.

2.3. EXPLORATORY OBJECTIVES

PART A AND B

- To evaluate the effect of Givinostat on single parameters of the clinical-haematological ELN response criteria [1].
- To evaluate the effects of Givinostat on PD markers.
- To evaluate the effects of Givinostat on spleen size (by MRI or CT scan) in patients with confirmed splenomegaly at baseline.
- To evaluate the effects of Givinostat on disease-related quality of life.
- To evaluate the effect of Givinostat on JAK2^{V617F} allele burden.
- To evaluate the reduction of the symptomatic treatment of pruritus.

PART B

- To evaluate the preliminary efficacy of Givinostat after 6 cycles of treatment according to the “new” ELN response criteria (i.e. the revised ELN response criteria).
- To evaluate the effect of Givinostat on single parameters of the “new” ELN response criteria (i.e. the *revised* ELN response criteria) [2].

3. STUDY DESIGN

3.1. GENERAL DESCRIPTION

This is a two-part, multicentre, open label, non-randomized, phase Ib/II study to assess the safety and tolerability, MTD and preliminary efficacy of Givinostat in patients with JAK2^{V617F} positive PV.

Part A is the dose escalation portion of the Study and, once the MTD has been established, Part B is commenced where the preliminary efficacy of Givinostat in PV patients will be established. Patients are enrolled either in **Part A** or **Part B** and transition from one part to the other is not allowed. Only PV patients from **Part A** assigned to the dose selected for **Part B** (MTD) can be counted towards the efficacy assessment in **Part B**.

Eligible patients for this Study have a confirmed diagnosis of PV according to the revised WHO criteria and the JAK2^{V617F} positivity. Only if the enrolment in **Part A** is slow (i.e. < 5 patients enrolled in 3 months), eligibility for this part of the Study could be expanded to all patients with cMPN.

After providing informed written consent before undertaking any protocol-related procedure, a unique

Document: PPD

Author: PPD

Version Number:

V2.2

Version Date:

21 March 2018

Template No: CS_TP_BS016 – Revision 3

Reference: CS_WI_BS005

Effective Date: 01May2012

Copyright © 2012 Quintiles Transnational Corp. All rights reserved.

The contents of this document are confidential and proprietary to Quintiles Transnational Corp. Unauthorized use, disclosure or reproduction is strictly prohibited.

patient identification code (i.e. patient screening ID which is a combination of his/her site ID, Study part ID and patient screening number, e.g. IT01-A01) is assigned to each patient which will identify the patient within his/her enrolment confirmation by Italfarmaco S.p.A. (Sponsor) or its designee (CRO) and can never be reused in case of screening failure. After the enrolment confirmation and the assignation of the dose level before the first drug intake, a unique patient identification code (i.e. patient ID which is a combination of patient screening number ID and dose level ID, e.g. IT01-A01-DL1) is assigned to each patient which will identify the patient throughout his/her participation in the Study and can never be reused in case of premature drop-out.

Study therapy is administered in 28 day cycles. In fact, the “cycle” is defined as 4 weeks of treatment.

Disease response is evaluated according to the clinico-haematological ELN criteria [1] after 3 and 6 cycles (i.e. at weeks 12 and 24, respectively) of treatment with Givinostat for both parts of the Study. All phlebotomies performed in the first 3 weeks of treatment are not been counted to assess the clinico-haematological response.

The Study will last up to a maximum of 24 weeks of treatment. However, after completion of the trial, all patients achieving clinical benefit are allowed to continue treatment with Givinostat (at the same dose and schedule) in a long-term study (Study N.: DSC/11/2357/44), providing that the long-term study has already received all necessary approvals in that specific country and site, and the study has already been initiated in that particular site.

Safety is monitored at each visit throughout the entire duration of the Study. Treatment is administered on an outpatient basis and patients are followed regularly with physical and laboratory tests, as specified in the protocol (see [Appendix A](#) and [paragraph 4.5.4](#) of the Study protocol version 3.0); in case of hospitalization, the treatment is continued or interrupted according to the Investigators’ decision.

3.2. PART A

Part A is the dose escalation part of this Study, evaluating the safety, tolerability and MTD of Givinostat in patients with JAK2^{V617F} positive PV.

In this part of the Study the first cycle of treatment is used to assess the safety and tolerability of Givinostat as well as PK/PD.

After the completion of the first cycle, the patients are treated for an additional 5 cycles.

Only PV patients from Part A assigned to the dose selected for Part B (MTD) can be counted towards the efficacy assessment in Part B.

The Dose Levels and the rules of escalation to the next dose are detailed in [Sections 4.1.1.3](#) and [4.1.1.4](#)

Document: PPD

Author: PPD

Version Number:

V2.2

Version Date:

21 March 2018

Template No: CS_TP_BS016 – Revision 3

Reference: CS_WI_BS005

Effective Date: 01May2012

Copyright © 2012 Quintiles Transnational Corp. All rights reserved.

The contents of this document are confidential and proprietary to Quintiles Transnational Corp. Unauthorized use, disclosure or reproduction is strictly prohibited.

of the Study protocol version 3.0 (see pages 46 and 47).

3.2.1. DEFINITION OF DOSE LIMITING TOXICITY (DLT)

DLT is defined as the following drug-related toxicity:

- Grade 4 haematological toxicities, or
- Grade 3 febrile neutropenia, or
- Grade ≥ 3 non-haematological toxicities with exception of:
 - a) Grade 3 diarrhoea without adequate supportive care lasting less than 3 days, and
 - b) Grade 3 nausea or vomiting without adequate supportive care lasting less than 3 days, or
- Any drug-related SAE, or
- Any toxicity that is clearly not related to disease progression or intercurrent illness requiring interruption of dosing for more than 3 days during the first cycle.

The severity of the above mentioned events is graded according to NCI Common Terminology Criteria for Adverse Events (CTCAE v. 4.03, 14th June 2010).

Only DLTs experienced during the first cycle of treatment are considered for dose escalation decisions. DLTs included all Adverse Events that are clearly not related to disease progression or intercurrent illnesses.

Patients who do not experience a DLT and miss more than 10% of the doses in Cycle 1 of Part A should be replaced (see [paragraph 4.6.4](#) of the Study protocol version 3.0).

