3.2.2.1. DOSE LEVELS (DLs) AND DOSE ESCALATION SCHEME

Dose escalation is conducted according to a standard 3+3 design, adopting a modified Fibonacci escalation schema [3, 4, 5]. Patients are enrolled in cohorts of 3 new patients (up to a maximum of 6) in rising dose levels (Table 1). Dose escalation to the next higher Dose Level (DL) can only occur after the third patient in the DL is followed for a minimum of 1 cycle after the first administration of study agent,

Document: PPD

Author: PPD

Version Number:

V2.2

Version Date:

21 March 2018

Template No: CS_TP_BS016 – Revision 3

Reference: CS_WI_BS005

Effective Date: 01May2012

Copyright © 2012 Quintiles Transnational Corp. All rights reserved.

The contents of this document are confidential and proprietary to Quintiles Transnational Corp. Unauthorized use, disclosure or reproduction is strictly prohibited.

and the current dose is determined to have an acceptable safety profile according to the following rules summarised in Table 2.

Table 1 – Dose escalation scheme for Givinostat mono-therapy in Part A

Givinostat daily dose	Givinostat dose level (DL)	DL used primarily to assess
50 mg b.i.d.	DL0	Safety, PK, PD*
100 mg b.i.d.	DL1	MTD, PK, PD
150 mg b.i.d.	DL2	MTD, PK, PD
200 mg b.i.d.	DL3	MTD, PK, PD
150 mg t.i.d.	DL4	MTD, PK, PD
200 mg t.i.d.	DL5	MTD, PK, PD

* DL previously demonstrated as safe.

The DL0 (i.e. 50 mg b.i.d.) was previously shown to be well tolerated in studies (see [Section 6 “Effects in humans”](#) of the Investigator Brochure Dossier related to ITF2357). Therefore, it is preferred to assign patients to the highest available dose level (i.e. DL1, DL2, DL3, DL4 and DL5) before assigning patients to DL0.

Intermediate Dose Levels (IDLs) and, consequently, additional DLs can be introduced to more accurately define the MTD.

Note that if a pregnancy occurs, the patient can be replaced and another patient in that DL should be recruited.

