3.4. TREATMENTS

3.4.1. TREATMENTS ADMINISTERED

Givinostat is supplied by the Sponsor or its designee as hard gelatine capsules for oral administration at the strength of 50 mg, and/or 75 mg, and/or 100 mg each.

Each capsule contains a granulate (obtained by wet granulation) composed of ITF2357, sodium starch glycolate, hydroxypropyl methyl cellulose (HPMC), sodium lauryl sulphate, lactose, magnesium stearate and colloidal silica.

The packaging consists of HDPE plastic bottles- closed with a PP screw cap, tamper evident - containing hard gelatine capsules of Givinostat. Each bottle contains:

- 30 capsules of 50 mg of Givinostat, or
- 30 capsules of 75 mg of Givinostat, or
- 15 capsules of 100 mg of Givinostat.

At each visit, patients receive a number of bottles sufficient to cover the period between two visits.

In **Part A** patients can be treated in DLs at the following starting daily doses of Givinostat:

Document: PPD

Author: PPD

Version Number:

V2.2

Version Date:

21 March 2018

Template No: CS_TP_BS016 – Revision 3

Reference: CS_WI_BS005

Effective Date: 01May2012

Copyright © 2012 Quintiles Transnational Corp. All rights reserved.

The contents of this document are confidential and proprietary to Quintiles Transnational Corp. Unauthorized use, disclosure or reproduction is strictly prohibited.

- 50 mg b.i.d.;
- 100 mg b.i.d.;
- 150 mg b.i.d.;
- 200 mg b.i.d.;
- 150 mg t.i.d.;
- 200 mg t.i.d..

Intermediate Dose Levels (IDLs) and, consequently, additional DLs can be used to establish the MTD (for more details, see [paragraph 4.1.1.3](#) of the Study protocol version 3.0).

Notably, the tested DLs to be considered for the MTD statistical analysis, are resumed in the **Table 1.1**.

Table 1.1 - Dose escalation of Givinostat performed in Part A

Givinostat daily dose	Givinostat dose level (DL)	DL used primarily to asses	Label for Tables, Listings and Figures (TLFs)
100 mg b.i.d.	DL1 (first three patients)	MTD, PK, PD	DL1
	DL1 (additional three patients)		DL1 expanded
2 capsules of 50 mg at the morning AND 1 capsule of 50 mg at the evening (i.e. 12 hours after)	DL6	MTD, PK, PD	DL6
50 mg b.i.d.	DL0	Safety, PK, PD*	DL0

* DL previously demonstrated as safe.

No patient will be treated at the DL2, none at DL3, none at DL4, none at DL5 in **Part A**, as per dose escalation scheme describe in the Study protocol and also summarised in the [section 3.2.2.1](#). of the present document.

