5.4. MAXIMUM TOLERATED DOSE ANALYSIS SET (MTD)

The MTD analysis set will include all patients who experienced DLTs in Cycle 1 of **Part A**, or who received at least 90% of the doses of study medication in Cycle 1 of **Part A**. The data regarding the Cycle 1 of **Part A** will be used to determine MTD from this analysis set.

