For TEAEs leading to discontinuation of Study drug, summaries of incidence rates (i.e. frequencies and percentages) by SOC and PT will be presented.

ADVERSE EVENTS LEADING TO DEATH

If any patients died during the Study, as recorded on the sections “EOS” and/or “AE” of the electronic CRF, the information will be presented in a summary table and a data listing.

TEAEs leading to death will be identified by using the following responses on the section “AE” of the electronic CRF:

- “Yes” at the question “Is this a serious event?” (death details);
- “Fatal” on the field “Outcome”;
- “Death related to AE” on the field “Severity”.

A summary of TEAEs leading to death by SOC and PT will be prepared.

All details of TEAEs leading to Death (date of death, autopsy performed and date of autopsy, if applicable, and death due to of Progression of the disease), recorded on “Death report” page on eCRF, will be listed only.

A case narrative for each death will be reported in the Clinical Study Report.

DOSE LIMITING TOXICITIES

A DLT is defined as one of the following drug-related toxicity:

- Grade 4 haematological toxicities, or
- Grade 3 febrile neutropenia, or
- Grade ≥ 3 non-haematological toxicities with exception of:
 - a) Grade 3 diarrhoea without adequate supportive care lasting less than 3 days, and
 - b) Grade 3 nausea or vomiting without adequate supportive care lasting less than 3 days, or
- Any drug-related SAE, or
- Any toxicity that is clearly not related to disease progression or intercurrent illness requiring interruption of dosing for more than 3 days during the first cycle.

The severity of the above mentioned events is graded by the Investigators according to CTCAE v. 4.03,

Document: PPD

Author: PPD

Version Number:

V2.2

Version Date:

21 March 2018

Template No: CS_TP_BS016 – Revision 3

Reference: CS_WI_BS005

Effective Date: 01May2012

Copyright © 2012 Quintiles Transnational Corp. All rights reserved.

The contents of this document are confidential and proprietary to Quintiles Transnational Corp. Unauthorized use, disclosure or reproduction is strictly prohibited.

dated 14th June 2010.

Only DLTs experienced during the first cycle of treatment (i.e. up to C1D28) of **Part A** are considered for dose escalation decisions. DLTs include all AEs that are clearly not related to disease progression or intercurrent illnesses. Patients who didn't experience a DLT and missed more than 10% of the doses in Cycle 1 of **Part A** are replaced.

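### In Cycle 1 of Part A the DLT, replacement and MTD-set thresholds do not meet, so a toxicity interruption of exactly 3 days can leave the DLT count and the MTD denominator

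*SAP*

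**What the plan says.** Three rules in the SAP apply to the same patient in Cycle 1 of Part A.

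- **DLT by interruption (section 3.2.1, repeated in 17.1).** A toxicity clearly not due to progression or intercurrent illness is a DLT when "requiring interruption of dosing for more than 3 days during the first cycle".
- **Replacement (section 3.2.1).** "Patients who do not experience a DLT and miss more than 10% of the doses in Cycle 1 of Part A should be replaced". Section 17.1 repeats this: "Patients who didn't experience a DLT and missed more than 10"% of the Cycle 1 doses are replaced. Neither place makes an exception for doses missed because of drug toxicity.
- **MTD set (section 5.4).** The set holds patients with a Cycle 1 DLT, or those "who received at least 90% of the doses of study medication in Cycle 1". The MTD is determined from this set.

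Table 2 (section 3.2.2.2) then acts only on the number of patients with a DLT at the level. Sections 15 and 15.1 class a patient without a DLT who missed more than 10% of Cycle 1 doses as insufficiently compliant.

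**The concern.** The DLT rule is set in days and the other two in percent of doses, and the limits do not coincide. A patient can be off drug because of toxicity for a time too short to be a DLT and too long to remain evaluable. A new patient then takes that place. Removal from the denominator therefore depends on the outcome that the cohort is meant to measure.

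The gap matters for this drug. Among haematological toxicities, only grade 4 events and grade 3 febrile neutropenia are DLTs by grade. Section 3.7 names thrombocytopenia as a known side effect and gives the observed platelet decrease as one reason for the choice of MTD. A non-serious grade 3 thrombocytopenia with a 3-day interruption is the kind of event that would fall between the rules.

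**Working it through.** **Inputs**

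- Cycle length 28 days: "Study therapy is administered in 28 day cycles" (section 3.1).
- Two doses a day at DL1: "100 mg b.i.d. DL1 MTD, PK, PD" (Table 1). Some planned levels are t.i.d.
- DL6: "2 capsules of 50 mg at the morning AND 1 capsule of 50 mg at the evening" (Table 1.1), so 2 dose times or 3 capsules a day.
- Limits: DLT if longer than 3 days; replaced if more than 10% missed; in the MTD set if at least 90% received.

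The SAP states no operating characteristics for Part A, so there is no figure to reproduce.

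**Step 1: where the limits fall.** Missed share = (days off × doses per day) / (28 × doses per day). At b.i.d. there are 28 × 2 = 56 doses, and 10% is 5.6 doses.

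| Continuous interruption | Missed (b.i.d.) | Share | DLT by interruption? | In MTD set? |
|---|---|---|---|---|
| 2.5 days | 5/56 | 8.9% | no | yes |
| 3 days | 6/56 | 10.7% | no | **no, replaced** |
| 3.5 days | 7/56 | 12.5% | yes | yes, as a DLT |

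The 3-day share is the same at t.i.d. and for DL6 counted in capsules (9/84 = 10.7%). If only 54 or 55 doses were scheduled (an assumption), 6 missed doses would be 11.1% or 10.9%. For one continuous b.i.d. interruption the gap is therefore exactly 3 days.

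**Step 2: repeated interruptions.** Two interruptions of 2 days each miss 8/56 = 14.3%. If the 3-day limit applies to each episode, this patient also falls in the gap. If days are added over the cycle, 4 days is a DLT and there is no gap. The SAP does not say which reading applies.

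**Step 3: effect on the 3+3 rule.** Let p be the chance of a DLT under the present rules and q the chance of a non-DLT toxicity that falls in the gap. Both are assumptions; the SAP gives neither. A level passes with 0/3, or with 1/3 followed by 0/3:

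f(x) = (1−x)³ + 3x(1−x)⁵

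Use x = p/(1−q) when gap patients are replaced, x = p+q when they count as toxicity, and x = p when they are kept as evaluable without a DLT. For p = 0.25 and q = 0.10:

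- replaced: x = 0.25/0.90 = 0.278, f = 0.377 + 0.164 = 0.54
- counted as toxicity: x = 0.35, f = 0.275 + 0.122 = 0.40
- kept as non-DLT: x = 0.25, f = 0.422 + 0.178 = 0.60

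| p | q | Replaced | Counted as toxicity | Kept as non-DLT |
|---|---|---|---|---|
| 0.10 | 0.10 | 0.89 | 0.71 | 0.91 |
| 0.20 | 0.05 | 0.69 | 0.60 | 0.71 |
| 0.25 | 0.10 | 0.54 | 0.40 | 0.60 |
| 0.30 | 0.10 | 0.43 | 0.31 | 0.49 |

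Replacement lies between the two alternatives in every row.

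**The case against.** **The gap is narrow.** Grade 4 haematological toxicity, febrile neutropenia of grade 3, nearly all non-haematological toxicity of grade 3 or more, and any drug-related SAE are DLTs whatever the interruption. What remains is lower-grade or non-febrile grade 3 haematological toxicity that is not serious, at one interruption length. This stands and limits how often the gap can matter.

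**DLTs are flagged on the CRF, and the protocol may say more.** Section 17.1 identifies DLTs by a yes/no question on the AE form, so an investigator could flag such an event, but the written definition gives no basis for doing so at 3 days. Section 3.2.1 refers replacement to protocol paragraph 4.6.4, which is not at hand and might separate reasons for missed doses. The SAP's own restatement does not.

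**The SAP already reports much of this.** Section 5 requires reasons for exclusion from each analysis set, and section 23 lists reasons for each interruption. But an exclusion reason of under 90% of doses would satisfy section 5 without showing that toxicity was the cause, and section 23 does not link its listing to the MTD set.

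**Three stronger readings are tempting and not supported.**

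- *That toxicity is hidden from the escalation decision.* It leaves the DLT count and the MTD set. The patient remains in the safety set (section 5.1), and the study team weighs the whole safety and tolerability profile (section 3.2.2.3). Section 3.7 records that with one DLT in six at DL1 the team still declined to escalate, citing the platelet decrease among its reasons.
- *That one such patient would have turned 1/6 at DL1 into 2/6.* Table 1.1 shows DL1 as three patients plus three more, and section 3.7 speaks of six treated there. No replacement at DL1 is evident. A replaced patient put back would also make seven treated, not six.
- *That replacement always makes a dose look more tolerable.* It does so only against counting these events as toxicity. Against keeping the patients as evaluable non-DLTs, it lowers the chance of passing.

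**Conclusion.** The point holds as a defect in how three rules fit together. A toxicity interruption of exactly 3 days that is not a DLT by another route misses 10.7% of doses, is not a DLT, leads to replacement and puts the patient outside the MTD set. Repeated shorter interruptions do the same if the 3-day limit is read per episode.

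The size cannot be given as one number. At p = 0.25 and q = 0.10 the pass probability is 0.54 with replacement, against 0.40 or 0.60 depending on how the event would otherwise be classed. Those rates are illustrative only. The SAP does not show that any patient fell in the gap, and its account of DL1 suggests that none was replaced there, so this is no evidence that the chosen MTD is wrong. It is a reason to reconcile the text and to show readers that the Part A result does not depend on the gap.

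**What to change.** 1. **Reconcile the rules.** Sections 3.2.1, 5.4 and 17.1 must agree on doses missed because of drug toxicity, including whether days off are counted per episode or over the cycle. Which rule applies is for the sponsor's clinical team.
2. **Report the exclusions.** In sections 5.4 and 17.1, add per dose level the number of patients replaced or excluded from the MTD set, and whether the missed doses were due to drug-related toxicity. The reasons are already collected for the section 23 listing.
3. **Add one MTD sensitivity table.** Keep patients excluded for drug-related toxicity in the denominator and show them both ways, as non-DLT and as toxicity, so that the table imposes no single DLT rule. Say how Table 2 is read when a level then has other than three or six patients, and state whether either version changes the Table 2 action.

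The cost is a few sentences and one extra table from data already held. The downside is a possibly less favourable count at some level. If no patient was excluded for toxicity, the table simply confirms the Part A result.
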